"Stop the stopwatch when you first begin to feel any pain-relieving effect whatsoever of the drug. That is, when you first feel a little relief. This does not necessarily mean that you feel completely better, although you might, but when you first feel any difference in the pain that you have now."

The participant will notify the Study Coordinator as soon as this stopwatch is stopped. The elapsed time on stopwatch A will be recorded in the case report form as the time to **first perceptible pain relief**. The participant will then be asked:

"Do you consider the relief you experienced meaningful?"

This answer will be recorded by the study coordinator in the case report form. If the participant answers "Yes" to this question, then meaningful pain relief is confirmed. The time recorded in the case report form for time to **meaningful pain relief confirmed will be the same time recorded as first perceptible pain relief.** The participant will not be given the second stopwatch. If the participant does not consider the relief to be meaningful, (by stating No), the participant will be given a second, covered stopwatch with instructions to:

"Stop this stopwatch when you have meaningful relief, that is, when the relief from the pain is meaningful to you."

The elapsed time on stopwatch B will be recorded in the case report form as time to **meaningful pain relief determined**. Unless meaningful pain relief is achieved, the participant will always have an active stopwatch in front of them.

If the participant never experiences first perceptible pain relief, they will retain stopwatch A for the entire 24-hour evaluation period. If the participant experiences first perceptible pain relief but not any meaningful pain relief (confirmed or determined), they will retain stopwatch B for the remainder of the 24-hour evaluation period.

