3.1 Handling of Missing Data

3.1.1 Handling of Missing Data for Efficacy Assessments

Use of Rescue Medication:

In all analyses, for participants who take rescue medication, all pain intensity scores after intake of rescue medication will be imputed by the worse of the baseline or the score assessed immediately before taking rescue medication. All pain relief after intake of rescue medication will be imputed by "no relief" (0).

Missing data for efficacy parameter:

If Participants have missing pain data (i.e., pain intensity or pain relief scores) within the 24 hours period for the collection of pain rating data, but nonetheless complete the 24-hour period, then any missing timepoints will be replaced by a time-weighted average of the previous and the next available values (i.e., a linear interpolation for missing values) of the pain data (pain intensity / pain relief score). Intermittent missing data will only be imputed using linear interpolation method and if needed round down to the nearest whole number for pain relief scores, whereas for the categorical pain intensity the value will be rounded up to the nearest whole number.

Interpolation Formula,

$$y = \frac{y_2 - y_1}{x_2 - x_1} (x - x_1) + y_1$$

Where, and if needed round down to the nearest whole number for pain relief scores, whereas for the categorical paint intensity the value will be rounded up to the nearest whole number. y = missing pain data to be imputed, x = respective timepoint of y. y_1 and y_2 = pre and post available pain score of the missing pain data.

 x_1 and x_2 = respective timepoints of y_1 and y_2 .

If Participants do not complete the pain intensity/pain relief assessments for the full 24 hours, then the primary analysis will be calculated up to the last available timepoint, with no imputation for later timepoints.

In a sensitivity analysis, Participants who drop out of the study early because of a related AE or lack of efficacy will have later missing timepoints imputed using a worst-observation-carried-forward (WOCF) method, in which their worst observation at baseline or any time thereafter is imputed. For Participants dropping out early for any other reason, a last-observation-carried-forward (LOCF) imputation will be used.

No imputation will be done for missing data on stopwatch assessments of perceptible and meaningful pain relief. Instead, if data are missing for those assessments, data will be censored as described in Section 4.1.

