The durations between two time points will be calculated using the actual post-dose times of the pain score measurement. If the actual time is missing, then the nominal planned time will be used.

Pain Relief:

Participants will assess their current pain relief using a 5-point scale as 0: No relief, 1: A little relief, 2: Some Relief, 3: A Lot of Relief, 4: Complete relief (categorical scale). Each Participant will be instructed to mark the number indicating his or her current pain relief.

The Participant is to record pain relief (5-point categorical rating scale) at given time points during the 24-hour period and immediately before first use of rescue medication.

Total Pain Relief (TOTPAR):

Total pain relief (TOTPAR) is calculated by multiplying the pain relief score at each time point by the duration (in hours) since the preceding time point and then summing these over the relevant period.

$$TOTPAR_{0-2} = \sum_{i=1}^{4} (T_i - T_{i-1}) * PAR_i$$
$$TOTPAR_{0-4} = \sum_{i=1}^{6} (T_i - T_{i-1}) * PAR_i$$
$$TOTPAR_{0-6} = \sum_{i=1}^{8} (T_i - T_{i-1}) * PAR_i$$
$$TOTPAR_{0-8} = \sum_{i=1}^{10} (T_i - T_{i-1}) * PAR_i$$

Private and Confidential Study No 22093 Date: MAR 11, 2024

$$TOTPAR_{6-12} = \sum_{i=8}^{14} (T_i - T_{i-1}) * PAR_i$$
$$TOTPAR_{0-12} = \sum_{i=1}^{14} (T_i - T_{i-1}) * PAR_i$$
$$TOTPAR_{12-16} = \sum_{i=14}^{16} (T_i - T_{i-1}) * PAR_i$$
$$TOTPAR_{16-20} = \sum_{i=16}^{18} (T_i - T_{i-1}) * PAR_i$$
$$TOTPAR_{12-24} = \sum_{i=14}^{20} (T_i - T_{i-1}) * PAR_i$$
$$TOTPAR_{16-24} = \sum_{i=16}^{24} (T_i - T_{i-1}) * PAR_i$$

Where, $T_0=0$, T_i is actual post-dose time, PAR_i is the Pain Relief score at post-dose time T_i for all i > 0.

Peak Pain Relief:

Peak pain relief is the highest observed value of pain relief experienced during post-dose assessments of the study.

Peak Pain Intensity Difference (Peak PID):

Peak pain intensity difference is the highest observed value of pain intensity difference calculated by formula given above in this section.

Time to first Perceptible Relief:

Time to first perceptible relief is the time when the Participant experiences any perceptible pain relief after administration of study drug and stops the first stopwatch. If it is not stopped, time will be censored at the time of last pain relief score assessment or at the first use of rescue medication, whichever comes first.

Time to meaningful relief:

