Time to meaningful relief is the time when the Participant experiences relief that is meaningful after the administration of study drug and stops the second stopwatch. If it is not stopped, time will be censored at the time of last pain relief score assessment or at the first use of rescue medication, whichever comes first.

Time to first perceptible relief confirmed by meaningful relief:

Time to first perceptible relief confirmed by meaningful relief is defined as the time to perceptible pain relief (the first stopwatch time) for those Participants who had confirmed meaningful pain relief immediately after first stopwatch and it will be time to meaningful pain relief (the second stopwatch time) for those Participants who did not confirm the meaningful relief before second stopwatch. If stopwatch is not stopped, time will be censored at the time of last pain relief score assessment or at the first use of rescue medication, whichever comes first.

Time to the First Use of Rescue Medication:

Time to first use of rescue medication for pain is defined as the time from first study drug administration to the first use of rescue medication. If rescue medication for pain is not taken, the time will be censored at the time of the last pain intensity score assessment.

Time to achieve complete pain relief:

Time to achieve complete pain relief is defined as the time from first study drug administration to the achieve complete pain relief. If complete pain relief not achieved, the time will be censored at the time of the last pain relief score assessment.

Cumulative proportion of Participants taking rescue medication:

The cumulative proportion of Participants taking rescue medication will be calculated as the cumulative number of Participants who taken rescue medication by a given timepoint divided by the number of Participants treated in respective treatment group.

Participants with 'at least a 2-point PID':

Participants with observed PID score greater than or equal to 2 at any post dose timepoints will be considered as 'at least a 2-point PID'. The same previous formula will be used to calculate the Pain intensity difference (PID).

Participant's Global Assessment of Investigational Product:

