The definitions and censoring rules are defined in Section 4.1. Median time will be compared between the treatment groups and placebo using a log-rank test stratified by baseline pain intensity (Categorical pain intensity), pair wise comparison will be made using Tukey-Kramer method and adjusted P-value will be reported. The summary statistics (25th percentile, Median, 75th percentile and it 95% CI) and overall K-M estimates with 95% CI will be presented by treatment groups. The analysis will be performed for the ITT Population.

Pain Intensity Difference (PID) and Pain Relief scores at 0.5, 1, 1.5, 2, 3, 4, 5, 6, 7, 8, 9, 10, 11, 12, 14, (16, 18, 20 if awake), 22 and 24 hours post-dose

The PID at each scheduled time point will be calculated using the formula specified in Section 4.1. Descriptive statistics (n, mean, SD, median, minimum, and maximum) will be presented by treatment groups.

Pain Relief score categories will be presented in the form of frequency counts and percentage by treatment groups and overall. Also, the pain relief score at each scheduled time point will be summarised using descriptive statistics (n, mean, SD, median, minimum, and maximum) by treatment groups. The analysis will be performed for the ITT Population.

A graphical illustration of the time effect curve (Time versus Mean PID / Mean pain relief score) will be presented.

Analysis of Peak Pain Intensity Difference (Peak PID)

The peak PID for each Participant will be identified using the description given in Section 4.1.

The Peak Pain Intensity Difference over the entire study (Peak PID0-24) will be summarized by treatment group using descriptive statistics (n, mean, SD, median, minimum, and maximum) and analyzed using an analysis of covariance (ANCOVA) model, which includes Peak PID0-24 as dependent variable, treatment as main effect and baseline pain intensity (Numerical Rating Score) as the covariate. The least square (LS) mean, standard error (SE) and 95% confidence interval (CI) of LS mean will be reported for each treatment group. In addition, the least square mean difference, SE, 95%

Confidence interval of LS mean difference and p-value for all pairwise treatment group (include placebo) comparisons will be reported. The analysis will be performed for the ITT Population.

Analysis of Peak Pain Relief

The peak pain relief for each Participant will be identified using the description given in Section 4.1.

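### A relief time that was not recorded is censored as if the stopwatch had never been stopped

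*SAP*

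**What the plan says.** SAP 3.1.1 treats stopwatch data separately from pain scores: "No imputation will be done for missing data on stopwatch assessments of perceptible and meaningful pain relief". The next sentence gives the replacement: "Instead, if data are missing for those assessments, data will be censored as described in" Section 4.1.

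SAP 4.1 has one censoring instruction, repeated for each of the three onset endpoints:

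- First perceptible relief: "If it is not stopped, time will be censored at the time of last pain relief score assessment". A further clause brings the censoring forward when rescue is taken earlier: "or at the first use of rescue medication, whichever comes first".
- Meaningful relief: the time at which the participant "stops the second stopwatch. If it is not stopped, time will be censored at the time of last pain relief score assessment", with the same rescue clause.
- Perceptible relief confirmed by meaningful relief: "If stopwatch is not stopped, time will be censored at the time of last pain relief score assessment", again with the rescue clause.

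SAP 7.7.2 adds no further rule: "The definitions and censoring rules are defined in" Section 4.1. Protocol 8.1.6 describes the participant for whom the rule was evidently written: "If the participant never experiences first perceptible pain relief, they will retain stopwatch A for the entire 24-hour evaluation period". Neither document mentions a watch that was stopped but whose reading is missing.

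**The concern.** Right-censoring says that the event had not yet happened at the censoring time. That is correct for a participant who never stopped the watch. It is false for one who is known to have had relief but has no recorded time: the event came before the censoring time, so the onset is left- or interval-censored. Following 3.1.1 to the letter keeps this participant in the risk set, counted as without relief, until rescue or the last relief rating.

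The trial already collects data that bound the onset. Protocol 8.1.6 schedules relief ratings at 0.5, 1, 1.5 and 2 hours and then hourly to 12 hours. It also has the coordinator record whether the first relief was meaningful. The plan uses neither for this purpose. The WOCF/LOCF sensitivity analysis in SAP 3.1.1 is written for later timepoints missing after early dropout, not for stopwatch times. SAP 7.7.2 and 7.7.3 analyse the stopwatch endpoints in the ITT population only, with no sensitivity analysis.

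At stake are the Kaplan-Meier onset curves, their medians, and the log-rank comparisons of onset.

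**Working it through.** The plan states no figure on this point, so there is none to reproduce. The check has three parts.

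**1. What the rule does to each kind of record**

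| What is on record | SAP 3.1.1 with 4.1 | What is actually known |
|---|---|---|
| Watch not stopped | Censored at rescue or last relief rating | No relief by then: correct |
| Stopped for relief, time recorded | Event at that time | Correct |
| Stopped or relief reported, time missing | Censored at rescue or last relief rating | Event happened earlier: wrong |
| Not known whether stopped | Censored at rescue or last relief rating | Cannot be settled from the stopwatch record |

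An invented example: relief rating 0 at 0.5 h, rating 2 at 1 h, first relief noted as meaningful, time not entered. The onset lies between 0.5 and 1 h. The SAP rule censors at about 24 h if there is no rescue, or at 6 h if rescue is taken at 6 h.

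**2. Size on the Kaplan-Meier curve**

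Inputs: 144 participants in each of the three naproxen-containing arms and 48 each on caffeine and placebo (Protocol 9.2, SAP 2.3). The share *m* of relief times that are lost is not in the documents, so it is assumed.

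With no earlier censoring, one lost reading lowers cumulative relief by 1/n from the true onset onward:

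- 1/144 = 0.7 percentage points
- 1/48 = 2.1 percentage points

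For a share *m* lost, the curve becomes F*(t) = (1 − m)F(t). At *m* = 1% and 2% that is 144 × 0.01 = 1.4 and 144 × 0.02 = 2.9 participants in a large arm, if all of them have relief.

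Suppose a proportion *p* of the arm ever gets relief, with exponential times among them. The median is then multiplied by ln(1 − 0.5/[p(1 − m)]) / ln(1 − 0.5/p):

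| p | m = 1% | m = 2% | m = 5% |
|---|---|---|---|
| 100% | 1.015 | 1.03 | 1.08 |
| 70% | 1.02 | 1.04 | 1.11 |
| 55% | 1.04 | 1.10 | 1.31 |

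Where rescue follows the lost onset, the participant leaves the risk set at rescue and the deficit is smaller from then on.

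**3. Effect on the comparison (illustration only)**

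Simulated log-rank test, 144 against 144, two-sided 0.05, unstratified and unadjusted. Assumed inputs: slower-arm median onset 0.75 h, hazard ratio 1.45, median time to rescue 8 h, 3,000 trials per setting. Power with no readings lost and with 2% lost in both arms:

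- All participants would reach relief: about 86% falls to about 71%. Placing each lost time at the first scheduled rating after onset keeps it at about 84%.
- 90% in each arm would: about 44% to 38%.
- 80% in each arm would: about 25% to 23%.
- 70% in each arm would: no detectable change.
- Settings where the arms also differ in the proportion relieved (70–80% against 85–90%, hazard ratio 1.2–1.45): a fall of 2 to 4 points, for example 93% to 91%.

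The large loss in the first setting arises because almost nobody is left at risk late, so a few false non-responders dominate the late risk sets.

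**The case against.** The other side has four arguments of substance.

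*The sentence in 3.1.1 may be only a cross-reference.* Since 4.1 covers only a watch not stopped, missing may simply mean that there is no stop time because there was no relief. That is a possible intention. The text, however, speaks of missing data without limit and directs all of it to 4.1, so a programmer following it would censor lost readings too.

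*Lost readings should be rare.* Under Protocol 8.1.6 the participant notifies the coordinator as soon as the first watch is stopped, and the time and the answer on meaningful relief go into the case report form. Protocol 10.1.9 provides for source data verification and, with 10.1.11, asks that reasons for missing data be documented. This stands, and it limits the likely size.

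*The consequence is small.* The endpoints are secondary and outside the SPID0-8 testing sequence. The same rule applies in every arm, and relief scores by timepoint are tabulated anyway. This stands too.

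*Replacing lost times can bring its own bias.* If every unknown record with a relief score of 1 became a stopwatch event, events would be created with no evidence that the watch was stopped. Censoring meaningful relief just before a known event would again be informative. Both objections are sound, and the fix below avoids both.

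A reader might also infer that affected participants always count as relief-free for the full 24 hours, or that the onset comparisons lose much of their power. The rescue clause rules out the first as a general statement. The second rests on assumed loss rates and on a model in which everyone eventually gets relief. The planned test is also not the one simulated: SAP 7.7.2 stratifies by baseline pain category and applies Tukey-Kramer adjustment.

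**Conclusion.** The point holds as a narrow defect in a stated rule. A participant known to have had relief, but with no recorded time, is right-censored after the event, at first rescue or the last relief rating. This shifts that arm's onset curve late by about 0.7 points per lost reading in a 144-participant arm or 2.1 points in a 48-participant arm, and by less where rescue comes first.

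The direction in a single arm does not depend on assumptions. The total size does, because the documents give no rate of lost readings; at an assumed 1–2% it would be roughly 1 to 3 participants in a large arm. If readings are lost at similar rates across arms, arms with more relief lose more events and differences shrink. With unequal rates the distortion could go either way.

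The primary endpoint and its test sequence are untouched. The documents do not support a claim that the onset conclusions will be materially wrong. This is a low-priority correction, worth making because it is cheap.

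**What to change.** Amend SAP 3.1.1 and 4.1 to separate three cases.

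1. **Watch not stopped for relief:** keep the present censoring. This includes a watch still running that is stopped only because rescue is given (Protocol 6.5.1).
2. **Record shows the watch was stopped for relief, or relief was reported, but the time is missing:** treat perceptible onset as lying between the last pre-rescue relief rating of 0 and the first of 1 or more, or set it at the latter. For meaningful relief, use the yes/no answer recorded under Protocol 8.1.6. If yes, use the same onset as perceptible relief. If no and the second reading is lost, treat it as an event bounded below by the first-watch time. Confirmed relief then follows from these two.
3. **Not known whether the watch was stopped:** keep the present rule in the main analysis and apply the relief-rating rule in a sensitivity analysis.

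Report the number of lost readings by arm and endpoint.

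The cost is a few sentences and a small derivation, with no new data. The downside is precision: the substituted time is only as fine as the rating schedule, which is 30 minutes in the first 2 hours and an hour from then to hour 12.

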3.1.2 Handling of Missing Data for Safety Evaluations

To handle missing or partial AE and concomitant medication dates, the following rules will be applied.

For Partial Start Dates:

- 1. If the year is unknown, then do not impute the date but assign a missing value.
- 2. If the month is unknown, then:
 - i. If the year matches the year of the dose date, then impute the month and day of the dose date.
 - ii. Otherwise, assign "January."
- 3. If the day is unknown, then:
 - i. If the month and year match the month and year of the dose date, then impute the day of the dose date.
 - ii. Otherwise, assign "01."

For Partial End Dates:

- 1. If the year is unknown, then do not impute the date but assign a missing value.
- 2. If the month is unknown, then assign "December."
- 3. If the day is unknown, then assign the last day of the month.

After implementing the rules above, to determine whether AEs (or medications) with missing start or stop dates are pre-treatment or on/after treatment, the following strategy will be used:

- 1. If the start date and stop date are both missing, then the most conservative approach is taken and the AE (or medication) is considered to be treatment emergent (or concomitant medication).
- 2. If the start date is missing but the stop date is not missing and is on or after the day of study dose administration, then the most conservative approach is taken and the AE (or medication) is considered to be treatment emergent (or concomitant medication).
- 3. If the start date is missing but the stop date is not missing and is before the day of study dose and after the date of signed informed consent, then the AE (or medication) is considered to be before treatment (or prior medication).
- 4. If the start date is not missing but the stop date is missing, then the most conservative approach is taken, and medication is considered to be concomitant while the AE is defined by start date.
- 5. If the Adverse Event Relationship flag is missing, the relationship for adverse event will be imputed and will be considered as "Yes". If the Adverse Event Severity flag is missing, the severity will be imputed and will be considered as "Severe".

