6.5 Prior and Concomitant Therapy

The following treatments are prohibited from screening and during the study:

- Use of any form of medication or herbal supplements, including GABA and turmeric, or curcumin, within 5 days of surgery that would confound the evaluation of the study product, until discharge from the study site;
- Use of acetaminophen, naproxen, hydrocodone/acetaminophen, ibuprofen, aspirin, or other NSAIDs or any other pain reliever (OTC or prescription) within 5 days before surgery;
- Use of alcoholic beverages after midnight prior to surgery and throughout the evaluation period;

All medications (prescription and nonprescription products, vitamin and herbal products) taken by the participant from 30 days prior to Screening to End of Trial (EOT) will be documented. The reported medications will be reviewed and evaluated by the Principal Investigator or designee to determine if they affect the participant's eligibility to participate in the study.

Page 33 of 67

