7.3 Medical History

A complete medical history, including a complete review of all current and past diseases will be done on screening visit. Medical history term will be coded using the Medical Dictionary for Regulatory Activities (MedDRA) version 25.0. and summarized by treatment group and overall, by frequency count and percentage of Participants in each system organ class (SOC), preferred term (PT) using Safety Population.

Participants will be counted only once at the preferred term (PT), only once at the system organ class (SOC), and only once at Participant level for the counting of total number of Participants with a medical history term. Counts will be presented in descending frequency unless otherwise specified.

Listings of medical history events for Participants in the Safety Population will be provided.

7.4 **Prior and Concomitant Medications**

Any medication other than study drug, either prescription drug or over the counter (OTC) will be treated as concomitant medication.

Prior Medications

For a Participant in the Safety Population, prior medications will include any medication taken prior to Participant's first dose of Study Medication.

Concomitant Medications

Concomitant medications are defined as prescribed medications and over the counter (OTC) preparations, including herbal preparations and vitamins, other than Study medication taken during the treatment phase.

Prior and concomitant medication will be categorized by preferred Term and anatomical-therapeuticchemical (ATC) classification (highest level available) per World Health Organization Drug Dictionary (WHODRUG B3 March 01, 2022) will be summarized by treatment group and overall, for the Safety Population.

The frequency count and percentage of Participants using each medication will be displayed. Participants who taken the same medication (in terms of PT) more than once will be counted only once for that medication.

Participants taking multiple prior / concomitant medication will be counted only once in summary table. If the Participant is taking medication prior to study drug administration and continues the same drug after study drug administration, then such Participants will be summarized in both prior and concomitant medication summary tables.

All prior and concomitant medications will be presented in a listing for the Safety Population.

7.5 **Protocol Deviation**

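### SAP 3.1.2 sets a partial start date to the dose date without checking the stop date, so a record that ended before dosing can be given a start after its stop

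*SAP*

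**What the plan says.** SAP 3.1.2 gives one set of rules for partial adverse event and medication dates. Two of the start-date rules use the dose date:

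- Month unknown (rule 2.i): "If the year matches the year of the dose date, then impute the month and day of the dose date".
- Day unknown (rule 3.i): "If the month and year match the month and year of the dose date, then impute the day of the dose date".

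Neither rule carries a condition on the stop date. Classification is a later stage, introduced by "After implementing the rules above, to determine whether AEs (or medications) with missing start or stop dates are pre-treatment or on/after treatment". Four steps follow:

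- Step 1 applies when both dates are missing.
- Step 2 applies when the start is missing and the stop "is on or after the day of study dose administration, then the most conservative approach is taken".
- Step 3 opens with "If the start date is missing but the stop date is not missing and is before the day of study dose". It adds that the stop must fall after consent, and it then gives before treatment, or prior medication.
- Step 4 applies when the start is present and the stop is missing: "medication is considered to be concomitant while the AE is defined by start date".

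SAP 7.4 defines the medication classes: "prior medications will include any medication taken prior to" the first dose, and concomitant medications are those used in the treatment phase. A medication begun before study drug and continued afterwards is to appear in both summary tables.

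Protocol 6.5 sets the collection window: all medications "taken by the participant from 30 days prior to Screening to End of Trial (EOT) will be documented".

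**The concern.** A default to the dose date is a reasonable cautious choice when nothing shows that the record ended before dosing. It is not reasonable when the stop date is known and lies before the dose. The stop date then proves that the start was earlier, and the rule overwrites that information with an impossible date.

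The records that could trigger this are plausible. Medications are collected from 30 days before Screening, and Screening can be up to 28 days before surgery. Most medications must have been stopped at least 5 days before surgery (Protocol 5.1, 5.2 and 6.5). Pre-dose stop dates are therefore the expected pattern. A participant who remembers when a medicine was finished but only roughly when it was begun produces exactly this combination.

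At stake is the accuracy of the prior and concomitant medication tables and listings.

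**Working it through.** The documents give no figure on this point, so the check applies the rules as written to test records. The dates are assumptions: dose 20 May 2023, and consent and Screening on 1 May 2023. UN means unknown.

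**General result.** Let D be the dose date and S a recorded stop with S < D. When rule 2.i or 3.i applies, the imputed start is D. Start minus stop is then D − S > 0 in every case. An enumeration over all dose days in 2023 agrees:

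- Day unknown, stop 1 to 28 days before dosing in the same month: 5348 of 5348 combinations are inverted.
- Month unknown, stop 1 to 58 days before dosing in the same year: 19459 of 19459 are inverted.

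These counts confirm the logic. They do not estimate how often it will happen.

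**Test records.**

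| Recorded start | Recorded stop | Imputed start | Start minus stop | Classification step |
|---|---|---|---|---|
| UN-MAY-2023 | 10 May 2023 | 20 May 2023 | 20 − 10 = +10 days | none applies |
| UN-UN-2023 | 10 May 2023 | 20 May 2023 | +10 days | none applies |
| UN-UN-2023 | 10 Apr 2023 | 20 May 2023 | 20 + 20 = +40 days | none applies |
| UN-APR-2023 | 10 May 2023 | 1 Apr 2023 | −39 days (no fault) | none applies |
| year unknown | 10 May 2023 | stays missing | – | step 3: prior |
| year unknown | 10 Apr 2023 | stays missing | – | none (stop before consent) |

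**Largest gap for a medication.** The collection window reaches back at most 28 + 30 = 58 days before surgery. With dosing on the day of surgery, the inversion for a medication inside that window is at most 58 days.

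**Classification of the inverted records.** Steps 1 to 3 need a missing start, and after imputation only a record with an unknown year still has one. Step 4 needs a missing stop. A record with an imputed start and a recorded stop therefore meets none of them, and the remaining text points two ways:

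- The imputed start is the dose day. Step 2 treats a stop on the dose day as on treatment, and step 4 dates adverse events by their start. By analogy the record is concomitant or treatment-emergent.
- Under the SAP 7.4 definitions, a medication that ended before the first dose is prior and was not used in the treatment phase.

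Rows 1 and 5 show the inconsistency. They have the same stop date, yet the record with less start information reaches a clear and correct class, and the record with more does not.

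**Ongoing medication.** Take an oral contraceptive, which is permitted, begun earlier in 2023 with month unknown and still in use. Rule 2.i gives a start of 20 May 2023, and step 4 makes it concomitant. If prior status is derived from the imputed start, the medication no longer precedes the dose and leaves the prior table. SAP 7.4 places it in both tables.

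**The case against.** The best defense is that this is a narrow drafting gap with a descriptive effect, and that more could be read into it than the text allows. Four stronger readings are tempting.

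1. *The SAP classes these records as concomitant or treatment-emergent.* It does not say so. The steps are limited to records with a missing start or stop, and a programmer who follows SAP 7.4 would call the medication prior. What is supported is a conflict within the text.

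2. *The less complete record is always handled correctly.* Step 3 also requires the stop to fall after consent. With a stop before consent, the year-unknown record has no rule either, as the last row of the table shows.

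3. *Pre-dose events will inflate the count of treatment-emergent events.* Protocol 8.3.1 sends occurrences that begin after consent but before study drug to the Medical History page, not the adverse event page. An event that began and ended before dosing would have to be on the wrong page and also have a partial start. Step 3 does provide for adverse events that stopped before dosing, so the route is not closed, but it is narrow.

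4. *Participants could lose Per Protocol status because an earlier analgesic appears as prohibited use on the dose day.* Use of prohibited medication is a listed ground for a major deviation. However, nothing in the SAP derives deviations from imputed dates. They are identified before database lock and classified before unblinding, and the investigator reviews reported medications for eligibility.

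It is also true that no planned test or endpoint uses these dates, and that no medication duration output is planned. What remains is the imputation itself: a stated rule, not a silence, that yields an impossible date whenever it meets a pre-dose stop.

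**Conclusion.** The point holds as a minor error in the imputation rules. Rules 2.i and 3.i give a start after the stop for every record they touch whose stop is before dosing. The classification of such a record is then inconsistent between SAP 3.1.2 and SAP 7.4. An ongoing medication with only the dose year known for its start can lose its prior status.

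The exposure is mainly the prior and concomitant medication tables and listings. The effect on adverse events is small, no effect on the Per Protocol population is shown, and the SPID0-8 analysis does not change. The number of affected records depends on how many partial start dates are collected, which the documents do not give.

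The inversion follows from the text alone. The effect on the tables assumes that the programs derive the prior and concomitant classes from the imputed dates.

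**What to change.** Add a guard to SAP 3.1.2:

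- Apply the end-date rules first. Use the dose date for a partial start only if the resulting stop date is missing or is on or after the dose date.
- Otherwise, impute a start no later than the stop date. Class the record as prior medication or pre-treatment event, whether the stop falls before or after consent. This extends the logic of step 3 to partial dates and closes its gap for stops before consent.
- State that a medication recorded as in use before dosing keeps its prior status under SAP 7.4 whatever its imputed start. If it continues after dosing, it is counted in both tables.

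Rows 1 to 3 of the table would then have a start no later than 10 May, 10 May and 10 April 2023 respectively, and all three would be prior. Row 6 would be prior as well.

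The cost is two or three sentences in the SAP and a small change to the date-imputation program. No data collection, sample size or efficacy analysis changes.
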